6.2.14. Visit 9/Safety Follow-up

- Symptom-directed physical examination, including assessment for potential vertebral fracture
- Collect blood for immunogenicity testing
- Record vital signs
- Height
- ECG
- All AEs, including SAEs, will be recorded from the time of signing of the informed consent and up to the 30 days after the last dose of study medication
- All subjects who remain antibody positive will continue to be followed for immunogenicity testing every 6 months until their result is antibody negative

6.2.15. Unscheduled Visit

If the subject returns to the clinic for an unscheduled visit (e.g., to follow-up on an abnormal laboratory test), the procedures performed at this visit will be recorded in the eCRF and source documentation.

6.3. Vital Signs and Physical Examinations

A complete physical examination (review of all body systems), height, weight, and vital signs assessment will be performed at screening.

A complete physical examination includes a review of the following systems: head/neck/thyroid, eyes/ears/nose/throat, respiratory, cardiovascular, lymph nodes, abdomen, skin, musculoskeletal, and neurological. Breast, anorectal, and genital examinations will be performed when medically indicated. After screening, any clinically significant abnormal findings in physical examinations should be reported as AEs.

Height and weight will be measured with shoes off. Height is to be measured using a wall mounted stadiometer. When height cannot be accurately measured such as in cases of severe kyphosis or loss of height from vertebral compression fractures, a documented historical height (i.e., from government IDs, medical records, etc.) may be used.

Vital signs include orthostatic blood pressure (systolic and diastolic), temperature (oral), heart rate, and respiratory rate. These will be assessed following a 5-minute rest (seated or supine) and before blood sample collection. At visits when study drug is administered at the site, vital sign assessments will be collected before the dose of study drug. Supine and standing blood pressure measurements will be performed at each visit during the Treatment Period.

6.4. 12-Lead Electrocardiogram

Standard, 12-lead ECGs will be performed. A hard copy of the ECG should be printed and signed by the Investigator at the site. Any abnormalities should be noted and clinical relevance should be documented. An ECG will be recorded immediately prior to dosing and 1 hour postdose during the Treatment Period.

6.5. Laboratory Evaluations

6.5.1. Clinical Laboratory Evaluations

Hematology, serum chemistry, and urinalysis will be collected at time points indicated in the Schedule of Assessments and Procedures in Table 3. All clinical laboratory blood and 24-hour urine samples will be sent to a central laboratory for analysis and testing. A list of study clinical laboratory tests is in Table 5.

Hematology	Serum Chemistry	Urinalysis (Dipstick) ^a	Additional Tests
Hemoglobin	Sodium	pH	PTH (1-84) ^b
Hematocrit	Potassium	Glucose	25-hydroxyvitamin D ^b
			1,25-dihydroxy vitamin D ^b
WBC count with	Chloride	Protein	BSAP
differential in absolute			
counts			
RBC count	Inorganic phosphorus	Ketones	Estradiol
MCV	Albumin	Bilirubin	l estosterone ^b
MCHC	Total protein	Blood	SHBG [®]
МСН	Glucose	Urobilinogen	$1SH (13 \text{ and Free } 14)^c$
Platelet count	BUN	Specific gravity	
	Creatinine	Nitrite	
	Uric acid	Leukocytes	
	AST		
	ALT		
	GGT		
	СРК		
	Alkaline phosphatase		
	Total bilirubin		
	LDH		
	Total Cholesterol		
	Triglycerides		
	Total calcium		

Table 5: Clinical Laboratory Tests

a. Clinic only, if required by PI send to central lab for microscopy

b. Only required at Screening and Visit 8 or early termination (Month 12 visit)

c. Only required at Screening. Reflex testing for T3 and Free T4 will be performed by the central laboratory if TSH is outside the normal limits. Reflex testing for bone-specific alkaline phosphatase will be performed by the central laboratory if serum alkaline phosphatase is outside the normal limits.

ALT = alanine aminotransferase; AST = Aspartate aminotransferase; BSAP = bone-specific alkaline phosphatase; BUN = blood urea nitrogen; CPK = Creatine phosphokinase; GGT = gamma-glutamyl transpeptidase; LDH = lactate dehydrogenase; MCH = mean corpuscular hemoglobin; MCHC = mean corpuscular hemoglobin concentration; MCV = Mean corpuscular volume; PTH = parathyroid hormone; RBC = red blood cell; SHBG = sex hormone binding globulin; TSH = thyroid stimulating hormone; WBC = white blood cell

In the event of medically significant, unexplained, or abnormal clinical laboratory test values, the test(s) should be repeated and followed up until the results have returned to within the normal range or an adequate explanation for the abnormality is found. Clinically significant changes in laboratory tests that occur during the course of the study are to be reported as AEs.

The clinical laboratory will clearly mark all laboratory test values that are outside the normal range and the Investigator will indicate the clinical relevance of these out-of-range values.

6.5.2. Serum Markers of Bone Metabolism

Blood samples will be taken to measure efficacy related markers of bone metabolism at Day 1, Month 1, Month 3, Month 6, and Month 12 or early termination. S-PINP and s-CTX will be measured in all subjects.

6.5.3. Immunogenicity Testing

Serum samples for immunogenicity testing will be collected at Day 1 (Visit 3), Month 1 (Visit 4), Month 3 (Visit 5), Month 6 (Visit 6), Month 9 (Visit 7), Month 12 (Visit 8), and the Follow-up Visit scheduled at 1 month after the last dose of study medication (Visit 9). Samples will be tested for the presence of binding anti-abaloparatide antibodies, including determination of antibody titer. Any positive samples will be tested for the potential to neutralize abaloparatide in a cell-based assay. Additionally, positive samples will be tested for cross-reactivity to endogenous PTH and PTHrP. Any subjects who show presence of antibodies at the Follow-up Visit scheduled at 1 month following the last dose of study medication (Visit 9) will be retested at 6-month intervals post-study until antibody status return to negative.

The serum samples for immunogenicity testing will be analyzed and reported separately. All the planned analyses related to the immunogenicity results and antibody status will also be reported separately.

6.5.4. Pharmacokinetic Testing

A blood sample for PK analysis of abaloparatide will be collected using a 5 mL K3 EDTA tube with 0.1 mg/mL aprotinin at each time point indicated in the PK sample collection schedule (Table 4).

6.5.5. Specimen Preparation, Handling and Storage

The procedures for the collection, handling, and shipping of clinical laboratory samples are specified in a separate Laboratory Manual provided to each clinical site.

6.6. Imaging Procedures

All imaging measurements (BMD according to DXA and QCT) will be performed according to the procedures outlined in the Imaging Charter and Imaging Manuals which will be provided as a separate document. A central imaging laboratory will be utilized for all DXA and QCT readings. QCT will be performed in a subset of subjects at a selected number of study sites.

6.6.1. Dual Energy X-ray Absorptiometry

All subjects will have areal bone density (aBMD) measurements taken via DXA of the lumbar spine, total hip, femoral neck, at Screening (Visit 1), wrist at Day 1 (Visit 3); spine, total hip, femoral neck, and wrist at Month 3 (Visit 5), Month 6 (Visit 7), and Month 12 (Visit 8). Lumbar spine scans must include L1 through L4. Hip scans will include the entire proximal femur to about 2 cm below the lesser trochanter. DXA bone density assessments will be performed at the forearm to measure BMD of the distal one-third radius and ultra-distal radius. For hip and wrist scans, the same side should be used for all scans at all visits. If a subject fractures a hip or forearm being examined during the study, no further scans of either hip or forearm will be acquired.

For screening purposes, DXA scans of the lumbar spine, total hip, and femoral neck taken up to 35 days prior to the beginning of the Screening Period may be used to determine study eligibility. DXA scans should be performed using a study-approved scanner (and read by the study central DXA reader) up to 35 days prior to the subject's Screening Visit.

6.6.2. Quantitative Computed Tomography

A subset of subjects at a selected number of study sites will have volumetric BMD (vBMD) measurements taken via QCT of the hip on Day 1 (Visit 3) and Month 12 (Visit 8).

6.6.3. Clinical and Radiologic Evaluation of Fractures

All spine radiographs will be performed according to the procedures outlined in the Imaging Charter and Imaging Manual which will be provided as separate documents. All subjects will have X-rays taken to document fractures of the lumbar and thoracic vertebrae at Screening to confirm entry criteria. Radiographs of the lateral thoracic and lumbar spine will include coverage of T3 to S1. The lateral spine radiographs will be assessed for prevalent and incident vertebral fractures using the Genant Semiquantitative Scoring method (Genant et al, 1993).

- Grade 0: Normal (approximately < 20% reduction in anterior, middle, or posterior height)
- Grade 1: Mild fracture (approximately 20%–25% reduction in anterior, middle, or posterior height)
- Grade 2: Moderate fracture (approximately 25%–40% reduction in anterior, middle, or posterior height)
- Grade 3: Severe fracture (> 40% reduction in anterior, middle, or posterior height)

Incident radiological vertebral fractures occur in vertebrae with an increase in SQ score ≥ 1 at a Follow-up Visit. New incident radiological vertebral fractures occur in vertebrae that are not fractured (i.e., SQ score of 0) at Screening. Worsening incident radiological vertebral fractures occur in vertebrae with prevalent (i.e., pre-existing) fractures at baseline. Subjects will also be clinically evaluated for vertebral and nonvertebral fractures (wrist, hip, rib, etc.) which occur during the study. Should a clinical fracture occur, X-ray images and reports associated with the fracture must be obtained and maintained in the subject's medical record.

All fractures will be identified and evaluated as part of the disease assessment and will be documented in the case report forms and source documents.

6.7. Discontinuation from the Study

Subjects may voluntarily discontinue from the study for any reason at any time.

Any subject who demonstrates decreases in $BMD \ge 7\%$ from baseline of this study at the lumbar spine or total hip will have the assessment repeated and, if confirmed, will be notified by the Investigator, and be withdrawn from the study. Subjects sustaining a radiologically confirmed incident vertebral or nonvertebral fragility fracture will be informed of the finding and will be counseled as to treatment options and may discontinue or choose to remain on the study. Those subjects who sustain an incident fracture during the study and elect to remain in the study will be asked to sign an additional informed consent document advising them of an increased risk for subsequent fracture.

Subjects who decide they do not wish to participate in the study further should return for the assessments indicated for the Month 12/Early Termination and 30 days later for the Month 13/Follow-up Visit in the Schedule of Assessments and Procedures (Table 3). If they fail

to return for these assessments for unknown reasons, every effort (e.g., telephone, email, and letter) should be made to contact them.

6.7.1. Withdrawal of Consent

Subjects may voluntarily withdraw consent to participate in the study for any reason at any time.

Withdrawal of consent occurs only when a subject does not want to participate in the study anymore **and** does not want any further visits or assessments **and** does not want any further study-related contact.

If a subject withdraws consent, the Investigator must make every effort to determine the primary reason for this decision and record this information. Further attempts to contact the subject are not allowed unless safety findings require communicating or follow-up.

6.7.2. Early Study Termination

The study can be terminated at any time for any reason by the Sponsor. Should this be necessary, subjects should be seen as soon as possible and treated as a prematurely withdrawn subject. The Investigator may be informed of additional procedures to be followed in order to ensure that adequate consideration is given to the protection of the subject's interests.

The Investigator will be responsible for informing IRBs/IECs of the early termination of the study.

7. ADVERSE EVENT AND SERIOUS ADVERSE EVENT DOCUMENTATION

7.1. Evaluation of Safety

Timely, accurate, and complete reporting and analysis of safety information from clinical studies are crucial for the protection of subjects and is mandated by regulatory agencies worldwide. All clinical studies sponsored by RADIUS will be conducted in accordance with Standard Operating Procedures (SOPs) that have been established to conform to regulatory requirements worldwide to ensure appropriate reporting of safety information.

All AEs are collected from the time of the informed consent until 30 days after last dose of investigational product. Where possible, a diagnosis rather than a list of symptoms should be recorded. All AEs should be captured on the appropriate AE pages in the eCRF and in source documents. The Investigator will assess all AEs for relationship to study drug. For information on the safety profile obtained to date for abaloparatide, please refer to the IB.

7.1.1. Adverse Event

An AE is any untoward medical occurrence in a clinical investigation subject administered a pharmaceutical product and that does not necessarily have a causal relationship with this treatment. An AE can therefore be any unfavorable and unintended sign (including an abnormal laboratory finding), symptom, or disease temporally associated with the use of a medicinal (investigational) product, whether or not related to the medicinal (investigational) product (ICH, 1995).

AEs include:

- Worsening (change in nature, severity, or frequency) of conditions present at the onset of the study
- Intercurrent illnesses
- Drug interactions
- Events related to or possibly related to concomitant medications
- Abnormal laboratory values (this includes significant shifts from Baseline within the range of normal that the Investigator considers to be clinically important)
- Clinically significant abnormalities in physical examination, vital signs, and weight

An abnormal laboratory value will not be assessed as an AE unless it requires a therapeutic intervention or is considered by the Investigator to be clinically significant.

7.1.2. Serious Adverse Event

A SAE is any AE that results in any of the following:

- Death
- Life-threatening: The term "life-threatening" in the definition of "serious" refers to an event/reaction in which the subject was at risk of death at the time of the

event/reaction; it does not refer to an event/reaction which hypothetically might have caused death if it were more severe.

- Required in-subject hospitalization or prolongation of existing hospitalization
- A persistent or significant disability/incapacity (i.e., substantial disruption of the ability to conduct normal life function)
- Congenital anomaly/birth defect

Important medical events that may not result in death, are life-threatening, or require hospitalization may be considered serious when, based upon appropriate medical judgment, they may jeopardize the subject and may require medical or surgical intervention to prevent one of the outcomes listed in this definition. Examples of such medical events include allergic bronchospasm requiring intensive treatment in an emergency room or at home, blood dyscrasias or convulsions that do not result in in-subject hospitalization, or the development of drug dependency or drug abuse.

All AEs of osteosarcoma will be reported as SAEs. All reports of osteosarcoma, regardless of causality or expectedness, will be expedited to the FDA within 15 days of receipt. MedDRA preferred terms include osteosarcoma, osteosarcoma metastatic, osteosarcoma recurrent, extraskeletal osteosarcoma, extraskeletal osteosarcoma metastatic, extraskeletal osteosarcoma recurrent.

All treatment-related SAEs must be followed until resolution (subject has returned to baseline status of health) or until stabilization (the Investigator does not expect any further improvement or worsening of the reported event).

7.1.3. Recording an Adverse Event

All AEs/SAEs will be entered into the electronic database.

Planned hospital admissions or surgical procedures for an illness or disease that existed before the subject was enrolled in the study are not to be considered AEs unless they occur at a time other than the planned date or the pre-existing illness or disease worsens after enrollment into the study.

Fractures identified during the study are not to be recorded as AEs unless the subject is hospitalized, the fracture is complicated, or the Investigator considers the fracture to be unrelated to the subject's underlying osteoporosis. All fractures will be identified and evaluated as part of the disease assessment and will be documented in the CRF and by collection of source documents.

For both serious and non-serious AEs, the Investigator must determine the intensity of the event and the relationship of the event to study drug administration (abaloparatide and placebo). Intensity for each AE will be defined according to the following criteria:

Intensity	Definition
Mild	Awareness of sign or symptom, but easily tolerated.
Moderate	Discomfort enough to cause interference with normal daily activities.
Severe	Inability to perform normal daily activities.

If the intensity of an adverse event changes within a day, the maximum intensity should be recorded. If the intensity changes over a longer period of time, the changes should be recorded as separate events (having separate onset and stop dates for each intensity).

Relationship to blinded study drug administration will be determined by the Investigator according to the following criteria:

Relationship	Definition
None	No relationship between the event and the administration of study drug. The event is related to other etiologies, such as concomitant medications or subject's clinical state.
Unlikely	The current state of knowledge indicates that a relationship to study drug is unlikely or the temporal relationship is such that study drug would not have had any reasonable association with the observed event.
Possible	A reaction that follows a plausible temporal sequence from administration of the study drug and follows a known response pattern to the suspected study drug. The reaction might have been produced by the subject's clinical state or other modes of therapy administered to the subject.
Probable	A reaction that follows a plausible temporal sequence from administration of the study drug and follows a known response pattern to the suspected study drug. The reaction cannot be reasonably explained by the known characteristics of the subject's clinical state or other modes of therapy administered to the subject.

For the purpose of safety analyses, all AEs that are classified with a relationship to study medication administration of possible or probable will be considered treatment-related events.

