7.1.4. Serious Adverse Event Reporting

Any SAEs that occur during the study from the time the subject signs the ICF until 30 days after the last dose of study medication must be reported within 24 hours of first awareness of the event using the SAE report form and emailing to [contact]. Data should also be entered in the clinical trial eCRF.

Treatment-related SAEs will be followed until resolution or stabilization. The reference safety information for this study is the IB, which will be provided under separate cover to all Investigators.

Any SAEs that occur at any time after completion of the study, which the Investigator considers to be related to study drug, must be reported to the Sponsor or its designee.

The Investigator must submit the SAE to the IRB/ IEC in accordance with 21 CFR parts 56 and 312 as well as with applicable local regulations. Documentation of these submissions must be retained in the site study file.

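### The fracture exception in Protocol Section 7.1.3 names only hospitalization among the seriousness criteria, so a serious outpatient osteoporotic fracture may go unrecorded as an AE and unreported as an SAE

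*Protocol*

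**What the plan says.** Protocol Section 7.1.3 gives fractures their own recording rule: "Fractures identified during the study are not to be recorded as AEs unless the subject is hospitalized, the fracture is complicated". A third exception covers a fracture that the investigator does not attribute to osteoporosis. The same paragraph sends the rest to the fracture record: "All fractures will be identified and evaluated as part of the disease assessment and will be documented in the CRF", with source documents collected as well. Neither the protocol nor the SAP says what makes a fracture complicated.

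Section 7.1.2 builds seriousness on AE status: "A SAE is any AE that results in any of the following". The list is death, threat to life, hospitalization, congenital anomaly and "A persistent or significant disability/incapacity (i.e., substantial disruption of the ability to conduct normal life function". A further paragraph covers important medical events, which "may be considered serious when, based upon appropriate medical judgment, they may jeopardize the subject".

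Two other sections bear on the point. Section 7.1.1 has a broad definition with no exception for fractures: "An AE is any untoward medical occurrence in a clinical investigation subject administered a pharmaceutical product". Section 7.1.4 says that any SAE from consent to 30 days after the last dose "must be reported within 24 hours of first awareness of the event using the SAE report form", again with no exception for fractures.

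**The concern.** Keeping non-serious endpoint fractures out of the AE data is a reasonable choice in an osteoporosis trial. The difficulty is that the exceptions bringing a fracture back in do not match the list that defines seriousness. A painful vertebral fracture managed at home can substantially disrupt a man's normal life, yet none of the three exceptions plainly covers it if it is put down to osteoporosis.

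Four things depend on whether such a fracture is recorded as an AE:

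- **Causality and intensity.** Sections 7.1 and 7.1.3 ask the investigator to assess these for AEs. Nothing asks for them for an exempt fracture. Causality is a live question here: the SAP (Section 4.5.3) makes orthostatic hypotension an adverse event of special interest, and Protocol Table 2 shows postural dizziness in 2 of 77 men in Phase 1. A fragility fracture after a drug-related fall could still be put down to osteoporosis.
- **Timing.** The 24-hour clock applies to SAEs. Ordinary eCRF entry (Section 9.9) need only be timely.
- **Tables.** The serious and treatment-related TEAE summaries in SAP Section 4.5.3 draw on AEs. The fracture analysis in SAP Section 4.3.2 has no summary by seriousness or causality.
- **Consistency.** With about 40 sites and an undefined term, similar fractures could be handled differently from site to site.

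**Working it through.** No arithmetic beyond a count applies. The check sets each seriousness criterion in 7.1.2 against the three exceptions in 7.1.3, for a fracture that the investigator attributes to osteoporosis.

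| Criterion in 7.1.2 | Named in 7.1.3? | How the fracture becomes an AE under 7.1.3 |
|---|---|---|
| Hospitalization | Yes | Directly |
| Death | No | Only if also admitted or called complicated |
| Life-threatening | No | Only if also admitted or called complicated |
| Disability or incapacity | No | Only if also admitted or called complicated |
| Important medical event | No | Only if also admitted or called complicated |
| Congenital anomaly | No | Not relevant to a fracture |

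Of six criteria, one is not relevant, which leaves 6 − 1 = 5. One of the five is named, so 5 − 1 = 4 are not. Fatal and life-threatening fractures will mostly involve admission. The realistic gap is therefore the disability and important-medical-event rows, for men treated as outpatients.

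For a fracture judged unrelated to osteoporosis there is no gap. The third exception makes it an AE, and every row of 7.1.2 then applies.

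Next, what the sections tell a site to do with a disabling outpatient osteoporotic fracture that is not called complicated:

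1. Under 7.1.1 it is an untoward medical occurrence, hence an AE.
2. Under 7.1.2 it is an AE with a listed outcome, hence an SAE.
3. Under 7.1.4 it must go on an SAE form within 24 hours.
4. Under 7.1.3 it is not to be recorded as an AE, and so goes only to the fracture CRF.

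Steps 1 to 3 and step 4 cannot all be followed. No sentence gives one precedence. A site that follows the specific instruction leaves the event out; a site that follows the general ones reports it.

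Last, what remains if the site follows 7.1.3. Clinical fracture assessment is scheduled from Pretreatment to Month 12 (Protocol Table 3). Images and reports must be obtained and all fractures documented (Section 6.6.3). SAP Section 4.3.2 compares new clinical fractures by arm in the ITT and PP populations: crude incidence, Kaplan-Meier estimates, hazard ratio and log-rank test, with follow-up to 30 days after treatment. The event is captured. The expedited report, the causality judgment and the place in the serious-TEAE tables may not be.

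**The case against.** The strongest reply is that 7.1.3 is only a recording rule. The paragraph before it says that certain planned admissions are not to be *considered* AEs, whereas fractures are not to be *recorded* as AEs. On that reading a disabling fracture still meets 7.1.1 and 7.1.2 and still has to be reported under 7.1.4. This stands to the extent that a reader who infers that such fractures are never AEs, or that the protocol exempts them from SAE reporting, goes further than the text. The documents contradict themselves; they do not grant a clear exemption. But the contradiction is itself the defect, because a site filling in forms will naturally follow the specific instruction.

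A second reply is that *complicated* is an open route not tied to admission, and that an investigator who thinks a fracture disabling or medically important would probably call it complicated. This will catch some cases. It does not close the gap, since the word can as naturally describe the injury as its functional consequence.

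A third is that fractures have other oversight. After an incident fragility fracture, discontinuation is offered following site consultation with the Medical Monitor, and a man who stays in signs a further consent (Section 4.3.1). A between-arm imbalance in clinical fractures would also appear in the efficacy analysis. All of this stands, and it is why the priority is low. None of it sets a 24-hour limit or asks for a causality assessment.

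It is also fair to say that SAE counts for any event depend partly on admission practice, because hospitalization is a general criterion. What is particular to fractures is that the routes not depending on admission are left unnamed.

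**Conclusion.** The concern holds in limited form. A non-hospitalized osteoporotic fracture that meets another criterion in 7.1.2, chiefly disability or important medical event, and is not called complicated may go unrecorded as an AE. It may then miss causality assessment, 24-hour reporting and the serious-TEAE tables, against 7.1.1 and 7.1.4.

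The documents give no rate for such fractures, so the number cannot be calculated. It is probably small: about 225 men are treated for 12 months, and Section 4.2 excludes T-scores of −3.5 or below, fragility fracture in the prior 12 months, and a history of severe or more than two moderate vertebral fractures. No efficacy conclusion depends on the point, and a reader should not infer that fracture data are lost.

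The conclusion assumes that no separate site instruction defines *complicated* or tells sites to report every fracture meeting a seriousness criterion. Neither the protocol nor the SAP mentions one.

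**What to change.** Reconcile 7.1.3 with 7.1.1, 7.1.2 and 7.1.4 by replacing the fracture sentence with a rule to this effect: a fracture need not be entered as an AE unless it (a) meets any seriousness criterion in Section 7.1.2, (b) is complicated, as defined in the protocol, or (c) is judged by the investigator to be unrelated to the underlying osteoporosis. Limb (a) makes hospitalization redundant as a separate exception. If limb (b) is kept, the term must be defined, or the variation between sites remains.

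Keep the separate fracture CRF for the efficacy endpoint, so that non-serious endpoint fractures stay out of the AE data as intended. The SAP tables need no change, because they will pick up the added events.

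The cost is one sentence and a definition in the protocol, matching eCRF guidance, and a few more SAE forms. Low priority.
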